10.4.3 ANALYSIS OF THE SECONDARY ENDPOINT(S)

The secondary endpoints listed below will be analyzed using ANCOVA linear regression models similar to the approach used in the primary endpoint:

- PROMIS 10a Fatigue total score
- Neurocognitive Battery total score
- ECog2 total score
- PASC Symptom Questionnaire total score
- ISI total score
- Sleep diary
 - Average nocturnal and 24-hour sleep duration and sleep efficiency
 - o Within-individual standard deviation of sleep onset
- Activity tracker
 - Within-individual standard deviation of sleep onset timing
 - o Average nocturnal and 24-hour sleep duration and efficiency

Comparisons of the treatment groups for endpoints with repeated measures outcomes over time will be investigated using mixed-effect linear models with GEE to account for correlated data within-participant.

If the null hypothesis is rejected for the primary outcome, then testing of the above secondary outcomes will be performed using the Hochberg method to control the type I error rate at 0.05. However, if the null hypothesis for the primary outcome is not rejected, then inferences on the secondary endpoints will be considered exploratory.

Safety endpoint. Safety endpoints include the proportion of participants who experience individual SAEs and the proportion who experience at least one or more SAEs. These will be analyzed in the safety population defined as the subset of mITT participants who confirm at least one administration of study intervention/control. Events of Special Interest (ESIs) will be summarized by the study intervention appendix and duration. The incidence of AEs/SAEs leading to discontinuation will also be summarized.

Other endpoints. Other secondary endpoints are either binary or continuous. Binary endpoints will be analyzed by logistic regression models to estimate the odds ratios [95% confidence intervals] between the treatment groups. Continuous endpoints will be analyzed using ANCOVA linear regression models.

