3 OBJECTIVES AND ENDPOINTS

The objectives, outcome measures, and endpoints listed in Table 1 are shared across all intervention appendices. Further details on outcome measures and endpoints are provided in Sections 8.8 and 10 and the Statistical Analysis Plan (SAP).

OBJECTIVES	OUTCOME MEASURES	ENDPOINTS
Primary		
Evaluate the efficacy of study intervention versus control on sleep-related daytime impairment, sleep disturbance, and/or sleep- wake rhythm disturbance	 See each appendix for which measure(s) is/are used: PROMIS 8a SRI (Sleep-Related Impairment) PROMIS 8b SD (Sleep Disturbance) (only Complex PASC-Related Sleep Disturbance) Activity tracker 	 Primary endpoint: change in total score from baseline to End of Intervention (EOI) of either 8a SRI or 8b SD The other measure becomes a secondary endpoint. Primary endpoint (only for Appendix B: Complex PASC- Related Sleep Disturbances): change in sleep onset variability from baseline to EOI
Secondary		
Evaluate the effect of study intervention versus control on fatigue	PROMIS 10a Fatigue	Change from baseline to EOI on PROMIS 10a Fatigue
Assess the effect of study intervention versus control on cognitive function	 Everyday Cognition 2 (ECog2) Neurocognitive Battery 	Change from baseline to EOI on cognitive function
Evaluate the effect of study intervention versus control on PASC-related symptoms	PASC Symptom Questionnaire	Change from baseline to EOI on PASC-related symptoms
Evaluate the effect of study intervention versus control on insomnia symptoms	Insomnia Severity Index (ISI)	Change in total score from baseline to EOI on the ISI
Compare the effect of study intervention versus control on sleep duration, efficiency, and timing	Sleep diary	Change from baseline to EOI in sleep onset variability, average nocturnal and 24-hour sleep duration, and absolute sleep midpoint
Compare the effect of study intervention versus control on sleep-wake patterns	Activity tracker	Change from baseline to EOI in average nocturnal and 24-hour sleep duration, sleep efficiency, and sleep midpoint

OBJECTIVES	OUTCOME MEASURES	ENDPOINTS
Exploratory		
Describe the effect of study intervention versus control on rebound symptoms	PROMIS 8a SRIPROMIS 8b SD	Change in total score of either 8a SRI or 8b SD from EOI to End of Study

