10.4.1 OVERALL STATISTICAL DESIGN

This study is a platform protocol designed to be flexible and consists of distinct symptoms of sleep disturbance using different interventional designs integrated into COVID-19 programs and subsequent treatment plans. For this study, data from all enrolled participants that receive the control intervention or treatment intervention will be included in the analyses. Between-group comparisons of the primary study endpoint, change from baseline in PROMIS SRI/SD T-scores (and sleep onset variability for Complex PASC-Related Sleep Disturbance), and clinically important secondary endpoints (eg, PROMIS 10a Fatigue, Neurocognitive Battery, etc.) will be analyzed using ANCOVA models. For endpoints that are categorized into binary secondary outcomes, logistic regression models will be utilized. Comparisons of the treatment groups for repeated measures outcomes over time will be investigated using mixed-

effect linear models with Generalized Estimating Equations (GEE) to account for correlated data withinparticipant.

Analyses of the primary endpoint measures, PROMIS SRI/SD T-scores (and sleep onset variability for Complex PASC-Related Sleep Disturbance), will require both the baseline and follow-up measurements. Participants missing one or both of their respective PROMIS SRI/SD measurements (or sleep onset variability) will not be included in the primary analysis cohort, ie, missing data on the primary endpoint will not be imputed in the primary analyses. However, sensitivity analyses will be conducted using imputation methods (eg, single or multiple imputation) to investigate the robustness of study findings. All testing hypotheses and estimated confidence intervals will be two-sided at a .05 significance level. The type I error rate of .05 for the secondary endpoints will be controlled using the Hochberg method.⁵⁰

Changes to the overall statistical design that occur prior to locking the study database will be detailed in the final SAP.

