14.1.1 PRIMARY OUTCOME MEASURES AND ENDPOINTS

Primary: PROMIS 8b SD to assess sleep disturbance and activity tracker to assess sleep onset variability

Secondary outcome to the Primary Objective: PROMIS 8a SRI

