14.8 STATISTICAL CONSIDERATIONS (APPENDIX LEVEL)

14.8.1 RATIONALE FOR SELECTION OF DOSE

Complex PASC-related Sleep Disturbances is a 2X2 factorial design. There will be two independent primary endpoints, namely (1) PROMIS 8b SD and (2) variability in sleep onset. Thus, each endpoint will be tested at .025 type I error rate to maintain the overall error rate at .05. Similar assumptions as in Appendix A (Section 13.7.1) will be used to calculate the statistical power for PROMIS 8b SD endpoint, except using type I error rate at .025 level. A total of 560 participants is needed to detect a 5-unit difference between groups with at least 90% power. For the variability in sleep onset with type I error rate of .025, a total sample size of 600 participants is needed. The study will have at least 90% power to detect an effect size between .35 and .45, assuming variability in sleep onset of SD = 70 minutes in the control group and roughly SD = 45 minutes in the intervention group. Thus, this study will require a total of 600 participants to maintain at least 90% power for both primary endpoints.

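### Section 10.4.3 applies one gate and one Hochberg list to both appendices: the list contains an Appendix B primary and omits declared secondaries, and the gate is undefined for Appendix B's two primaries

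*Protocol*

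**What the plan says.** Section 10.4.3 lists the endpoints to be analysed by ANCOVA and then sets the gate: "If the null hypothesis is rejected for the primary outcome, then testing of the above secondary outcomes will be performed using the Hochberg method", with error controlled at 0.05. The next sentence makes secondary inference exploratory if the primary null is not rejected. Section 10.4.1 gives the level as well: "The type I error rate of .05 for the secondary endpoints will be controlled using the Hochberg method".

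Appendix B (section 14.8.1) does not have a single primary: "There will be two independent primary endpoints, namely (1) PROMIS 8b SD and (2) variability in sleep onset". On alpha it says: "Thus, each endpoint will be tested at .025 type I error rate to maintain the overall error rate at .05". Section 14.1.1 confirms where the second primary is measured: "Primary: PROMIS 8b SD to assess sleep disturbance and activity tracker to assess sleep onset variability".

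Under the activity tracker, the 10.4.3 list includes "Within-individual standard deviation of sleep onset timing". For the PROMIS form that an appendix does not use as its primary, Table 1 says: "The other measure becomes a secondary endpoint". Sections 10.4.2, 13.1.1 and 14.1.1 agree. That form does not appear in the 10.4.3 list.

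**The concern.** Hochberg thresholds depend on how many endpoints are in the family and which ones. A family that includes one of the trial's own primaries and leaves out declared secondaries can therefore change which secondary claims succeed. This affects both appendices, because the non-primary PROMIS form and the midpoints are missing from each.

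In Appendix B the gate adds a second problem. If one primary is rejected and the other is not, the confirmatory sentence and the exploratory sentence of 10.4.3 both apply. The protocol does not say whether one or both must succeed, or how much alpha then passes to the secondaries. Whether a secondary result counts as confirmatory would be open at exactly the outcome that the alpha split was designed to allow.

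**Working it through.** **1. Alpha split.** .025 + .025 = .05, so section 14.8.1 is right for the two primaries. With independent endpoints the exact figure is 1 − .975² = .0494.

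**2. The two lists.** Cognition is counted as two measures (ECog2 and the battery). Nocturnal and 24-hour duration are counted separately.

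| Endpoint | 10.4.3 list | Table 1 secondary |
|---|---|---|
| Fatigue, battery, ECog2, PASC symptoms, ISI | 5 | 5 |
| Diary: nocturnal duration, 24-hour duration, onset variability | 3 | 3 |
| Tracker: nocturnal duration, 24-hour duration, efficiency | 3 | 3 |
| Diary efficiency | 1 | 0 |
| Tracker onset SD | 1 | 0 (primary in Appendix B) |
| Non-primary PROMIS form | 0 | 1 |
| Diary midpoint, tracker midpoint | 0 | 2 |
| Total | 13 | 14 |

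The shared items number 5 + 3 + 3 = 11. Table 1's diary objective mentions efficiency, but its endpoint column for the diary does not.

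**3. Effect of a primary inside the family.** Hochberg compares the k-th largest p-value with .05/k. Suppose the tracker onset result is clearly non-significant and has the largest p-value. It takes rank 1, and each of the other 12 moves down a rank, from .05/k to .05/(k+1):

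- largest true secondary: .05 becomes .025
- second largest: .025 becomes .0167
- smallest: .05/12 = .0042 becomes .05/13 = .0038

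In the other direction, an onset result with .025 < p ≤ .05 fails as a primary. Hochberg can reject it as a secondary only at rank 1, which requires all 13 p-values to be at or below .05. With all secondaries null this occurred in at most 0.001% of simulated trials.

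**4. The gate, if either success opened the full .05.** Take one comparison with one primary truly effective and certain to be rejected, and the other primary and all secondaries null. A false claim then needs a false rejection of the second primary (at most .025) or of a secondary (at most .05):

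- bound: .025 + .05 = .075
- independent events: 1 − .975 × .95 = .0738

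Simulation: 400,000 trials, two-sided tests, equicorrelated normal statistics. The list is as written: 12 null secondaries plus the second primary's own p-value. The last row uses a 14-endpoint family without the tracker onset item. Correlations are assumed, since the protocol gives none.

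| Correlation | 0 | .3 | .5 |
|---|---|---|---|
| Combined error, either success opens .05, list as written | .069 | .063 | .054 |
| Secondary family alone at .05 | .049 | .045 | .038 |
| Combined error, both primaries required, same scenario | .025 | .025 | .025 |
| Combined error, .025 passed on, 14 secondaries | .049 | .046 | .041 |

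Monte Carlo error is about .0004 on each figure.

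**5. Why passing on the rejected alpha works.**

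- Both primaries null: any false secondary claim requires a false primary rejection first, so the error is at most .05.
- One null: at most .025 + .025 = .05.
- Neither null: at most .05.

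As with any use of Hochberg, this assumes its usual dependence conditions hold within the family.

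**The case against.** A reader might infer that one success at .025 releases the full .05 and inflates the error rate. The protocol contains no such rule. The gate's singular wording can equally mean that both primaries must be rejected, and then the combined error stays at or below .05. The protocol also states .05 for the primary pair and .05 for the secondaries separately, never expressly for both together, and the secondary family taken alone stays within .05. These points stand, so the inflation can only be reported as conditional.

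A reader might also take the duplicated endpoint as an easy way to rescue a failed primary. It is not, because every listed p-value would have to be at or below .05. The likelier harm is to the true secondaries.

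Nor does section 10.4.1, with its general statement that "All testing hypotheses and estimated confidence intervals will be two-sided at a .05 significance level", contradict Appendix B. It is a platform-wide rule, and the appendix overrides it explicitly for its own primaries.

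Two further defences are weaker. Gate mechanics are often left to the SAP, and 10.4 refers to it. But the list conflicts with Table 1 and the appendices inside the protocol itself, which is not detail awaiting the SAP. The non-primary PROMIS form could also fall under the sentence in 10.4.3 on other secondary endpoints. That gives it an analysis model but leaves it outside the protected family, although Table 1 calls it a secondary without qualification.

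**Conclusion.** The point holds as a specification error in 10.4.3. The Hochberg family is wrong on any reading: it holds one Appendix B primary and leaves out three endpoints that Table 1 declares secondary, with 11 endpoints shared between lists of 13 and 14. The gate is undefined in Appendix B when exactly one primary is rejected.

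Any inflation depends on reading the gate as opened by either primary at the full .05, and on wanting control across primaries and secondaries together. On that basis the bound is .075, and the simulated rate falls from .069 to .054 as the assumed correlation rises from 0 to .5. These figures are for one intervention comparison and do not address multiplicity across the two factors of the 2x2 design. The primary conclusions are not affected.

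**What to change.** In section 10.4.3:

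- Give each appendix its own Hochberg family, identical to Table 1. Remove tracker sleep-onset SD. Add the non-primary PROMIS form (8b SD in Appendix A, 8a SRI in Appendix B) and the diary and tracker sleep midpoints.
- Remove diary sleep efficiency, or add it to Table 1's endpoint column, so that the two lists agree. The same choice applies to tracker sleep-onset SD if it is wanted as an Appendix A secondary.
- For Appendix B, state that the secondary family for an intervention is tested at the alpha of that intervention's rejected primaries: .025 if one, .05 if both, and exploratory if neither.

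Reporting 97.5% intervals beside the .025 tests of the Appendix B primaries is optional.

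The cost is wording only, with no extra participants or data, and it should be settled before unblinding. The statistical price is fewer confirmatory secondary claims in Appendix B when only one primary succeeds: with 14 endpoints the smallest p-value would face .025/14 = .0018 rather than .05/14 = .0036.

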10.4.4 ANALYSIS OF THE EXPLORATORY ENDPOINT(S)

Exploratory analysis will include analysis of sleep disturbance rebound, (as measured by PROMIS & SRI and PROMIS & SD), rebound sleep-wake patterns (as measured by the activity tracker), symptom burden, HRQOL, autonomic dysfunction, post-exertional malaise, viral and immune biomarkers, and healthcare utilization. Symptom burden analysis will be presented with consideration to subgroups by baseline symptoms, racial and ethnic subgroup, gender, acute COVID-19 severity, and timing after acute infection. Forest plots will be utilized for subgroup analyses on the primary endpoint. For participants who received study-issued PAP devices, PAP device adherence data will be analyzed in relationship to baseline symptoms, racial and ethnic subgroup, gender, and acute COVID-19 severity; adherence will be explored as a potential intervention effect modifier in this group. Refer to the SAP for details.

10.4.5 PLANNED INTERIM ANALYSES

Interim evaluation of clinical and key safety endpoints will be performed approximately quarterly, with additional meetings or conference calls scheduled as needed. An independent, NIH-appointed, DSMB will monitor participant safety and review the performance of the trial.

The primary goal of these interim analyses is to ensure the safety of the participants enrolled in the trial and evaluate the accumulating endpoints data by treatment group in order to make assessments of futility. As a general guideline, statistical boundaries (stopping rules) for futility will be generated using Lan and DeMets beta-spending functions.⁵¹ The actual boundaries (and frequency of looks) will be calculated at the precise information time (percent of enrolled participants with 10-week follow-up) when the DSMB convenes for a meeting. These statistical boundaries will need to be considered by the DSMB in light of the totality of clinical risk/benefit. The first futility analysis will be planned to occur when the study enrolls at least 50% of the targeted sample size. If the statistical futility boundary has been crossed, then the unblinded statistical team needs to provide the DSMB with the conditional probability (CP) under 2 scenarios: (1) CP under the current observed trend and (2) CP under the "best"

alternative, ie, under the sample size assumed effect-size. Typically, these CPs range between 0.10 and 0.20, indicating a futile study when CP <0.10 under scenario 1 and CP <0.20 under scenario 2.

Additionally, interim monitoring may involve a review of participant recruitment, compliance with the study protocol, status of data collection and completion, as well as other factors that reflect the overall progress and integrity of the study and may inform changes in eligibility criteria.

There are no plans to stop a study early for efficacy in this platform protocol. Because PASC presentations and outcomes are highly varied, an important study objective is to estimate the effect of treatment on a wide range of participant-relevant outcomes. If the study were to be stopped early with less than the full sample size, it would decrease precision and reduce the study's ability to characterize treatment risks and benefits based on important secondary effectiveness and safety outcomes. It would also limit the collection of data that are critical for planning future trials in similar patient populations.

11 SUPPORTING DOCUMENTATION AND OPERATIONAL CONSIDERATIONS

11.1 REGULATORY, ETHICAL, AND STUDY OVERSIGHT CONSIDERATIONS

11.1.1 INFORMED CONSENT PROCESS

11.1.1.1 INSTITUTIONAL REVIEW BOARD (IRB)

The protocol, informed consent form(s) [ICF(s)], recruitment materials, and all participant materials will be submitted to the IRB(s) of record for review and approval. This approval must be obtained before any participant is enrolled. Any amendment to the protocol will require review and approval by the IRB(s) before being implemented in the study. All changes to the consent form will also be IRB-approved and a determination will be made regarding whether previously consented participants need to be reconsented.

11.1.1.2 CONSENT PROCEDURES AND DOCUMENTATION

All consenting will occur either via an electronic consent process or a paper process. Consent forms describing in detail the study intervention/control, study procedures, and risks and benefits will be given to participants, and documentation of informed consent is required before starting study procedures. Informed consent is a process that is initiated before an individual agrees to participate in the study and continues throughout the individual's study participation. Consent forms will be IRB-approved. Participants will be allowed to carefully read and review the consent form and ask questions prior to signing. Participants will be provided with the study team's contact information. This will allow them to communicate with the site investigators (or their delegate), receive further explanations of the research study, and ask questions that may arise.

Participants should be given time to think about the study and discuss the study with the study team and their family members prior to agreeing to participate. Participants will sign the informed consent document before any procedures are done specifically for the study. Participants may withdraw consent at any time during the study. A copy of the informed consent document will be provided to the participants for their records. The rights and welfare of the participants will be protected by emphasizing to them that the quality of their medical care will not be adversely affected if they decline to participate in this study.

The study team will distinguish between the desire to discontinue study intervention and the desire to withdraw consent for study follow-up (per Section 7).

11.1.2 STUDY DISCONTINUATION AND CLOSURE

This study may be temporarily suspended or prematurely terminated if sufficient reasonable cause exists. Written notification, which documents the reason for study suspension or termination, will be provided by the sponsor to study participants, site investigators, the central IRB, and the US FDA. Study participants will be contacted, as applicable, and be informed of changes to the study visit schedule.

Circumstances that may warrant termination or suspension include, but are not limited to, the following:

- Determination of futility
- Determination of unexpected, significant, or unacceptable risks to participants
- Insufficient compliance with protocol requirements
- Data that are not sufficiently complete and/or evaluable

The study may resume once concerns about safety, protocol compliance, and data quality are addressed, and satisfy the sponsor, IRB, and/or FDA.

11.1.3 CONFIDENTIALITY AND PRIVACY

Participant confidentiality is strictly held in trust by the participating investigators, their staff, and the sponsor(s) and their agents. This confidentiality is extended to cover the testing of biological samples in addition to the clinical and private information relating to participants. Therefore, the study protocol, documentation, data, and all other information generated will be held in strict confidence. No information concerning the study or the data will be released to any unauthorized third party without the prior written approval of the sponsor. The study participant's contact information will be securely stored in the clinical study database.

Study participant research data, which is for purposes of statistical analysis and scientific reporting, will be transmitted to and stored at the CT-DCC. The study data entry and study management systems used by clinical sites and by research staff will be secured and password protected. At the end of the study, all study-related data storage systems will be archived according to local processes.

